#### **7.6. Other Safety Measures**

A data listing will be provided for the results of all pregnancy tests conducted in the study. Post-treatment anti-cancer therapies will be listed for applicable subjects.

## 8. PHARMACOKINETIC (PK) ANALYSES

### 8.1. PK Sample Collection

PK plasma samples will be collected for andecaliximab PK at 30(± 15) minutes after the end of infusion on Day 1 of Cycle 1, prior to dosing and 30(± 15) minutes after the end of infusion on Day 1 of Cycles 2, 3, 5, 7, and every 3 cycles thereafter, at the EOT and EOS visits.

CCI

### 8.2. Estimation of PK Parameters

PK parameters will be estimated using Phoenix WinNonlin® software using standard noncompartmental methods. The linear/log trapezoidal rule will be used in conjunction with the appropriate noncompartmental model, with input values for dose level, dosing time, plasma concentration, and corresponding real-time values, based on drug dosing times whenever possible.

All predose sample times before time-zero will be converted to 0.

For area under the curve (AUC), samples BLQ of the bioanalytical assays occurring prior to the achievement of the first quantifiable concentration will be assigned a concentration value of 0 to prevent overestimation of the initial AUC. Samples that are BLQ at all other time points will be treated as missing data in WinNonlin. The nominal time point for a key event or dosing interval ( $\tau$ ) may be used to permit direct calculation of AUC over specific time intervals. The appropriateness of this approach will be assessed by the PK scientist on a profile-by-profile basis.

Pharmacokinetic parameters such as  $AUC_{\tau}$ ,  $\lambda_z$  and  $t_{1/2}$  are dependent on an accurate estimation of the terminal elimination phase of drug. The appropriateness of calculating these parameters will be evaluated upon inspection of PK data on a profile-by-profile basis by the PK scientist.

### 8.3. PK Parameters

PK parameters will be generated for all subjects in the PK substudy analysis set.

CCI

CCI

### 8.4. Statistical Analysis Methods

Individual subject concentration data for andecaliximab, oxaliplatin, and 5-FU will be listed and summarized using descriptive statistics by treatment. Summary statistics (n, mean, StD, coefficient of variation [%CV], median, min, max, Q1, and Q3) will be presented for individual subject concentration data by time point.

Individual concentration data listings and summaries will include all subjects in PK analysis set. The sample size for each time point will be based on the number of subjects with nonmissing concentration data at that time point. The number of subjects with concentration BLQ will be presented for each time point. For summary statistics, BLQ values will be treated as 0 at predose and one-half of the LLOQ for postdose time points.

Individual subject PK parameters (PK substudy analysis set) for andecaliximab, oxaliplatin, and 5-FU will be listed and summarized using descriptive statistics by treatment. Summary statistics (n, mean, StD, coefficient of variation [%CV], median, min, max, Q1, and Q3) will be presented for individual subject PK parameters by treatment. Moreover, the geometric mean, 90% CI, and the mean and StD of the natural log-transformed values will be presented for individual subject PK parameter data.

Individual PK parameter data listings and summaries will include all subjects in PK substudy analysis set. The sample size for each PK parameter will be based on the number of subjects with nonmissing data for that PK parameter.

The following tables will be provided for each analyte by treatment:

- Individual subject concentration data and summary statistics (PK analysis set)

- CCI

The following figures may be provided for each analyte by treatment (PK analysis set):

- Mean ( $\pm$  StD) concentration data versus time (on linear and semilogarithmic scales)
- Median (Q1, Q3) concentration data versus time (on linear and semilogarithmic scales)
- Individual subject concentration versus time (on linear and semilogarithmic scales)

Individual, mean, and median postdose concentration values that are  $\leq$  LLOQ will not be displayed in the figures and remaining points connected.

The following listings will be provided

- PK sampling details by subject, including procedures, differences in scheduled and actual draw times, and sample age will be provided in listings (PK analysis set).
- CCI [REDACTED]

## 9. IMMUNOGENICITY ANALYSES

### 9.1. ADA Sample Collection

Serum samples for anti-andecaliximab antibody will be collected prior to dosing on Day 1 of Cycles 1, 2, 3, 5, 7, and every 3 cycles thereafter, EOT, EOS, and 30-day Safety Follow-Up visits.

### 9.2. Statistical Analysis Methods

Immunogenicity of andecaliximab will be evaluated based upon the positive ADA rate. The number and percentage of subjects exhibiting positive ADA status, defined as ADA presence in serum confirmed in validated assay and reported by bioanalytical laboratory, at each specified time point will be summarized. The number and percentage of subjects exhibiting positive ADA status at any post-andecaliximab time point will also be summarized.

The time to ADA onset will also be assessed, and it is defined as the time interval from the date of first dose of andecaliximab to the date positive ADA status is first achieved. The analyses of time to ADA onset will be based on the subjects in the immunogenicity analysis set who have negative ADA status at baseline and achieve positive ADA status at post baseline. Summary statistics (n, mean, StD, coefficient of variation [%CV], median, min, max, Q1, and Q3) will be presented.

The impact of ADA on andecaliximab PK may be evaluated as appropriate. Individual subject andecaliximab predose concentration data may be summarized using descriptive statistics by ADA status (positive or negative) of the same time point. Summary statistics (n, mean, StD, coefficient of variation [%CV], median, min, max, Q1, and Q3) will be presented by ADA status. The number of subjects with concentration BLQ will be presented for each time point. For summary statistics, BLQ values will be treated as 0 at predose. Individual subject andecaliximab predose concentration data versus ADA results may be plotted (on linear and semilogarithmic scales). PK plasma samples meeting below criteria will be included in this analysis:

- Collected on Cycle 3 Day 1 or later
- Collected 288 – 384 hours (12 to 16 days) post most recent dose

A by-subject listing for ADA status at each time point and the titer for subjects with positive ADA status will be provided by subject ID number and time point in chronological order.

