### **3.1.6. Immunogenicity Analysis Set**

The Immunogenicity Analysis Set will include all randomized subjects who received at least 1 dose of andecaliximab and have at least 1 nonmissing postdose antidrug antibody (ADA) status reported. This is the primary analysis set for all immunogenicity analyses.

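### Time to ADA onset (SAP 9.2) is summarised only among observed converters, with no censoring, so it is conditional on seroconversion and may largely reflect follow-up length if ADA is infrequent and steady, or slow in onset

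*SAP*

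**What the plan says.** SAP 9.2 defines time to ADA onset as "the time interval from the date of first dose of andecaliximab to the date positive ADA status is first achieved". It restricts the analysis to subjects in the Immunogenicity Analysis Set "who have negative ADA status at baseline and achieve positive ADA status at post baseline". For the output, "Summary statistics (n, mean, StD, coefficient of variation [%CV], median, min, max, Q1, and Q3) will be presented". It gives no censoring rule, Kaplan-Meier estimate or cumulative incidence for this variable.

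The same section also reports the number and percentage positive at each time point, a by-subject listing of ADA status, and an ever-positive rate: "The number and percentage of subjects exhibiting positive ADA status at any post-andecaliximab time point will also be summarized".

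The Immunogenicity Analysis Set (SAP 3.1.6) requires at least one andecaliximab dose and that subjects "have at least 1 nonmissing postdose antidrug antibody (ADA) status reported". Samples are taken "prior to dosing on Day 1 of Cycles 1, 2, 3, 5, 7, and every 3 cycles thereafter, EOT, EOS, and 30-day Safety Follow-Up visits" (SAP 9.1). Under Protocol 3.4, 3.6 and 6.6, treatment and study participation end at progression, among other reasons, so the length of sampling differs between subjects.

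Protocol 8.7 plans only counts and percentages of positive and negative results by time point. Time to onset is an addition in the SAP. Neither document states an expected ADA rate or how quickly ADA arises.

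**The concern.** Time to ADA onset is a time-to-event variable with unequal follow-up. A baseline-negative subject who is still negative when sampling stops carries information: onset, if it was to come, was later than that date. SAP 9.2 discards that subject, so entry to the analysis depends on the outcome. Among those kept, no onset time can exceed the subject's own sampling time.

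The result is a valid description of the subjects who were seen to convert. It does not estimate when treated, baseline-negative subjects develop ADA. Read that way, it puts onset too early. It would also differ between two studies with the same immunogenicity but different progression times. At stake is the interpretation of one immunogenicity table, for example when judging how soon exposure might be affected. No efficacy result depends on it.

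**Working it through.** **No ADA figure to reproduce.** The documents give no ADA incidence or onset time, so ADA kinetics below are assumptions varied over a range. Only the follow-up model comes from the plan.

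**Inputs from the plan.** Control median PFS 9 months and PFS hazard ratio 0.7, so the andecaliximab median is 9/0.7 = 12.86 months. Accrual is 18 months, minimum follow-up 18 months, dropout 10% per year, with 215 subjects per arm (SAP 1.3). Cycles last 28 days (Protocol 3.3). With the SAP 9.1 schedule, post-baseline samples fall 28, 56, 112, 168, 252, 336 ... days after first dose, plus the end visits.

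**Check on the borrowed inputs.** These assumptions give 321 to 322 expected PFS events (plan: 322). Power is Φ(√322/2 × |ln 0.7| − 2.144) = Φ(3.200 − 2.144) = 85.4% (plan: 85%). The follow-up model is consistent with the SAP.

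**Mechanism.** Let λ be a constant ADA hazard and μ a constant hazard of sampling ending. Onset time, given that it is observed, is exponential with rate λ + μ, so its mean is 1/(λ + μ). When λ is much smaller than μ this is about 1/μ, which is follow-up. When λ is much larger it is about 1/λ, which is onset speed. With μ = 0.7 × ln 2/9 = 0.0539 per month:

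- 12-month incidence 2%: λ = −ln(0.98)/12 = 0.0017, mean 18.0 months.
- 12-month incidence 20%: λ = −ln(0.80)/12 = 0.0186, mean 13.8 months.

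The formula ignores data cut-off, dropout and visit timing, so it overstates the means. It shows the mechanism, not the size.

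**Simulation.** 2,000,000 subjects on the SAP 9.1 schedule. Sampling ended at the earliest of progression, dropout and a data cut-off 18 to 36 months after entry, followed by the 30-day visit. Mean time to the end of sampling, before that visit, was 12.9 months.

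Steady ADA rate:

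| 12-month incidence | Ever positive | Mean among converters (months) | Median (months) |
|---|---|---|---|
| 2% | 2.3% | 11.0 | 8.6 |
| 5% | 5.7% | 10.9 | 8.3 |
| 10% | 11.1% | 10.7 | 8.3 |
| 20% | 21.6% | 10.1 | 8.3 |
| 40% | 40.3% | 8.9 | 8.3 |
| 60% | 56.7% | 7.6 | 5.5 |
| 80% | 71.6% | 5.9 | 3.7 |
| 95% | 84.2% | 4.0 | 3.7 |

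The median repeats at 8.3 months because that is a visit day: 252/30.4375 = 8.28.

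Only 10% of subjects able to form ADA, with varying onset speed in that group:

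| Latent median onset (months) | Mean among converters (months) | Median (months) |
|---|---|---|
| 0.5 | 1.3 | 0.9 |
| 1 | 2.0 | 1.6 |
| 2 | 3.2 | 1.8 |
| 4 | 5.1 | 3.7 |
| 8 | 7.2 | 5.5 |
| 12 | 8.3 | 5.6 |

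ADA kinetics held fixed, with only the PFS median moved from 4.5 to 18 months:

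- Steady rate, 5% at 12 months: mean 6.6 to 11.9 months; ever positive 3% to 7%.
- Susceptible 10%, latent median 1 month: mean 1.8 to 2.0 months.
- Susceptible 10%, latent median 12 months: mean 5.4 to 8.9 months.

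**Reading.** With infrequent, steady ADA, a tenfold rise in 12-month incidence moves the mean by 11.0 − 10.1 = 0.9 months, while the change in PFS moves it by 11.9 − 6.6 = 5.3 months. With common ADA, or early ADA in a susceptible minority, the summary responds to onset speed. With slow onset, truncation by follow-up returns.

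**The case against.** Four objections deserve weight.

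1. A reader might infer that the mean and median generally reflect sampling length and barely respond to onset speed, so that rare, slow ADA and frequent, fast ADA would look alike. The documents do not support this. It needs ADA that is infrequent (about 20% or less at 12 months) and steady, or slow in onset, and the plan gives no rate or kinetics. Under a steady rate the mean runs from 11.0 months at 2% incidence to 4.0 at 95%. In a susceptible 10% it runs from 1.3 to 8.3 months as latent onset slows. This objection stands, and the point is limited accordingly.

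2. A reader might take the size from the simple formula, which gives a mean of about 18 months at low incidence. That ignores cut-off and dropout; with them the mean is about 11 months. This also stands.

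3. SAP 9.2 already reports percentages positive by time point and ever positive, lists ADA status by subject, and says openly that the onset summary covers converters. So rare and frequent ADA would be told apart (2.3% against 21.6% ever positive in the first table). This stands in part. The percentage at a time point describes prevalence among those still sampled, and the ever-positive percentage is not adjusted for follow-up: it moves from 3% to 7% above with ADA kinetics unchanged. Neither gives cumulative incidence by a fixed time.

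4. Kaplan-Meier has its own assumptions. Sampling stops at progression or death, which may be informative or better treated as a competing event, and onset is known only to within the visit interval, up to 12 weeks after Cycle 7. This stands as a condition on the fix, not a reason to leave the gap.

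**Conclusion.** The point holds in a limited form. SAP 9.2 drops never-positive subjects instead of censoring them, so the mean and median describe onset conditional on observed seroconversion and are truncated by each subject's sampling time. That follows from the text alone.

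The size depends on assumed kinetics. If ADA is infrequent and arises at a roughly steady rate, the converters-only mean is about 10 to 11 months whether 12-month incidence is 2% or 20%, and follow-up length largely sets it; slow onset leads to the same problem. If ADA is common, or arises early in a susceptible minority, the summary follows onset speed. The documents cannot say which applies, which is a reason to specify a method that does not depend on knowing.

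These figures rest on the design PFS, dropout and accrual assumptions and on sampling continuing until progression. The consequence is small: one descriptive table, with no test, alpha, sample size or efficacy conclusion attached. It is a worthwhile improvement, not a flaw that threatens the trial.

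**What to change.** Add to SAP 9.2: in all subjects of the Immunogenicity Analysis Set who are ADA-negative at baseline, estimate cumulative ADA incidence by Kaplan-Meier at fixed times (for example 3, 6 and 12 months) with confidence intervals, censoring never-positive subjects at their last ADA sample. State whether progression and death are treated as non-informative censoring or as competing events; in the latter case use a cumulative incidence function. Keep the present summary, labelled as conditional on observed seroconversion.

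Cost: a sentence or two and one table. The sample dates and ADA results are already collected, and the SAP already uses Kaplan-Meier for OS and PFS. Downsides: a median may not be reached if ADA is rare (hence the fixed times), onset is known only to within the visit interval, and the censoring assumption must be stated and defended.

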## **10. BIOMARKER ANALYSES**

Biomarker analyses will be described in the biomarker analysis plan (BAP)

## **12. SOFTWARE**

SAS® (SAS Institute Inc., Cary, NC) is to be used for all programming of tables, listings, and figures.

WinNonlin® (Pharsight Corporation, Mountain View, CA) is to be used for all PK analyses.

### 13. SAP REVISION

Revision Date (DD MMM YYYY)	Section	Summary of Revision	Reason for Revision
27 SEP 2018	2.4, 3.4	Primary (OS) and secondary (PFS and ORR) efficacy endpoints will be examined in subgroups defined by baseline tumor PD-L1 status (positive vs. negative). This is a new analysis which was not specified in the protocol (Section 2.4) and the analysis is described in Section 3.4.	Add a new subgroup analysis.

**Appendix 1. List of Laboratory Tests for Safety Summary**

Serum Chemistry	Hematology	Coagulation
Sodium	White Blood Cell Count	PT/INR
Potassium	Hemoglobin	aPTT
Chloride	Hematocrit	
Glucose	Platelet Count	
BUN	ANC	
Creatinine a	Neutrophils	
ALT	Lymphocytes	
AST	Monocytes	
Alkaline phosphatase		
Total bilirubin		
Total protein		
Albumin		
Calcium		
Magnesium		
Phosphate		
Lipase		
Bicarbonate		

a Estimated creatinine clearance (CLcr)/glomerular filtration rate will be calculated based on the Cockcroft-Gault formula using actual body weight:  $CL_{cr} \text{ (mL/min)} = (140 - \text{age [years]}) * \text{weight (kg)} / (\text{serum creatinine [mg/dL]} * 72)$ . If the subject is female, multiply the quantity by 0.85.

**Appendix 2. List of Participating Country and Geographic Region**

Country	Region	
1	Australia	Asia Pacific
2	Belgium	Europe
3	Colombia	Latin America
4	Czech Republic	Europe
5	France	Europe
6	Germany	Europe
7	Hungary	Europe
8	Italy	Europe
9	Peru	Latin America
10	Poland	Europe
11	Romania	Europe
12	Spain	Europe
13	Turkey	Europe
14	United Kingdom	Europe
15	United States	North America
16	Chile	Latin America

### **Appendix 3. Details for Testing Efficacy Endpoints**

This appendix provides details for testing multiple efficacy endpoints at interim and final analyses.

The final analysis will occur when 286 overall survival (OS) events have been observed. Two formal interim analyses are planned: the futility interim analysis and the efficacy interim analysis will be performed when approximately 33.3% and 66.7% of OS events have occurred, respectively.

[figure not shown]
#### **Futility Interim Analysis**

The end point of the futility interim analysis is OS. The futility analysis will occur approximately after 95 OS events (33.3% of the information relative to the final analysis) have been observed in the ITT population. The analysis will perform a stratified log-rank test for OS in the ITT population. A non-binding futility rule will be implemented. Based on the analysis results, the IDMC may recommend terminating the study for lack of efficacy if the predictive power (PP) on OS in ITT population is  $< 14\%$ . Otherwise, the study will be continued.

Predictive power is defined as a weighted average of the conditional power; the weighting function is determined by the sampling distribution of the observed hazard ratio based on the data at the interim analysis {[Lan 2012](#)}. When exactly 95 OS events are observed at the interim, this futility rule of  $PP < 14\%$  corresponds to observing an OS hazard ratio (HR)  $> 0.95$  in the ITT population.

[Appendix Figure 1](#) presents the operating characteristics of futility rule at the interim of 95 OS events with futility boundary of 0.95. When the true hazard ratio is 0.7, the probability of terminating the study early is 7%. On the other hand, when the true hazard ratio is 1, indicating lack of efficacy, the probability of terminating the study early is 60%.

## Appendix Figure 1. Probability of Early Stop due to Futility

### Efficacy Interim and Final Analysis

In the efficacy interim and final analysis, the primary and secondary endpoints will be tested sequentially in the following gatekeeping order: the primary OS endpoint, then the secondary PFS endpoint, and finally the secondary ORR endpoint. Specifically:

- At the efficacy interim analysis, the OS event point will be tested at one-sided alpha level of 0.006. If the OS endpoint is not rejected, the study will continue to final analysis. If the OS endpoint is rejected, the IDMC would recommend early stop for efficacy. Furthermore, the PFS endpoint will be tested at one-sided alpha level of 0.016. Only if the PFS endpoint is rejected, the ORR endpoint will be tested at one-sided alpha level of 0.016.
- At the final analysis, the OS event point will be tested at one-sided alpha level of 0.023. If the OS endpoint is rejected, the PFS endpoint will be tested at one-sided alpha level of 0.016. If the PFS endpoint is also rejected, the ORR endpoint will be tested at one-sided alpha level of 0.016.

This gatekeeping testing strategy is summarized in the table below. Overall, this testing strategy employs O'Brien-Fleming boundary for the primary OS endpoint and the Pocock type boundary for the secondary PFS/ORR endpoints. The testing strategy controls the overall one-sided family-wise type I error to be at 0.025, equivalent to two sided 0.05 by appropriately adjusting for multiplicity in the efficacy interim and final analyses.

**Appendix Table 1. Gate-keeping Decision Boundaries for Efficacy Analysis**

Efficacy Analysis	Event (%)	One-sided Decision Boundary		
		OS	PFS (After OS boundary is crossed)	ORR (After PFS boundary is crossed)
Interim	191 (66.7%)	0.006	0.016	0.016
Final	286 (100%)	0.023	0.016	0.016

In the following scenarios we will provide detailed justification for this testing strategy. During efficacy interim and final analysis, type I error could occur in the following non-overlapping scenarios:

- 1) Reject  $H_{01}$  when  $H_{01}$  is true
- 2) Reject  $H_{01}$  and  $H_{02}$  when  $H_{11}$  and  $H_{02}$  is true
- 3) Reject  $H_{01}$ ,  $H_{02}$  and  $H_{03}$  when  $H_{11}$ ,  $H_{12}$ , and  $H_{03}$  is true

where  $H_{ij}$  ( $i=0$ : null,  $i=1$ : alternative) are the hypothesis for the  $j$ th endpoint (1 = primary OS, 2 = secondary PFS, 3 = secondary ORR).

**Scenario 1**

The type I error rate is controlled by the O'Brien-Fleming (OF) boundaries on the primary OS endpoint.

**Scenario 2**

We herein justify that the use of 1-sided significance level of 0.016 for the testing of secondary PFS endpoint at both the interim and final analyses will control the Type I error rate at 0.025 one-sided. We follow the methods in Hung et al (2007) {Hung 2007} and Tamhane et al (2010) {Tamhane 2010}.

Per Hung et al {Hung 2007}, the one-sided type I error rate in Scenario 2 in the hierarchical testing strategy is:

$$\alpha_2 = \Pr(T_{11} > C_{11}, T_{21} > C_{21} | H_{02}) + \Pr(T_{11} \leq C_{11}, T_{12} > C_{12}, T_{22} > C_{22} | H_{02}) \quad (1)$$

where  $T_{jk}$  and  $C_{jk}$  are the test statistic and critical value, respectively, for the  $j$ th endpoint (1 = primary OS, 2 = secondary PFS) and the  $k$ th analysis (1=interim, 2=final). Accordingly, (1) can also be written as:

$$\alpha_2 = \Pr(Z_{11} > z_{11}, Z_{21} > z_{21} | H^{02}) + \Pr(Z_{11} \leq z_{11}, Z_{12} > z_{12}, Z_{22} > z_{22} | H^{02}) \quad (2)$$

where  $Z_{jk}$  and  $z_{jk}$  are the corresponding test statistics and critical values expressed in the setting of the standard normal distribution (ie, after standardization). Equation (2) can be evaluated analytically and we prove in the following that in the scenario 2, under the proposed testing strategy, the one-sided type I error rate is controlled at 0.025.

[figure not shown]
It can be derived that  $\tilde{Z} = (Z_{11}, Z_{21}, Z_{12}, Z_{22})$  follows the multivariate normal distribution below:

$$\begin{pmatrix} Z_{11} \\ Z_{12} \\ Z_{21} \\ Z_{22} \end{pmatrix} \sim MVN \left( \begin{pmatrix} \mu_{11} \\ \mu_{12} \\ \mu_{21} \\ \mu_{22} \end{pmatrix}, \begin{pmatrix} 1 & \rho & \rho\sqrt{t} & \rho\sqrt{t} \\ \rho & 1 & \rho\sqrt{t} & \rho\sqrt{t} \\ \rho\sqrt{t} & \rho\sqrt{t} & 1 & \rho \\ \rho\sqrt{t} & \rho\sqrt{t} & \rho & 1 \end{pmatrix} \right) \quad (3)$$

where  $(\mu_{11}, \mu_{12})$  and  $(\mu_{21}, \mu_{22})$  are the normalized mean treatment effects on the primary and secondary endpoints, respectively, for data up to the interim and final analysis. The mean treatment effects between the interim and final analysis can be related by the information fraction  $t$ :  $\mu_{j1} = \mu_{j2}/\sqrt{t}$  where  $j = 1, 2$ . Under the assumption of Scenario 2, the mean treatment effect on the primary OS endpoint  $(\mu_{11}, \mu_{12})$  is positive representing the alternative hypothesis, and the mean treatment effect on secondary PFS endpoint  $(\mu_{21}, \mu_{22})$  is set to  $(0, 0)$  under the null hypothesis.  $\rho$  denotes the correlation between the primary and the secondary test statistics at each analysis stage, ranging from 0 to 1, assuming a non-negative correlation.  $t = 0.667$  denotes the planned information fraction at the interim efficacy analysis. The one-sided OF boundaries for the primary endpoint are given by  $z_{11} = z_{0.006}$  and  $z_{12} = z_{0.023}$ . Thus, equation (2) can be evaluated using the `pmvnorm` function in the R package `mvtnorm` based on the mean and covariance structure specified in equation (3).

Appendix Figure 2 shows the analytically calculated type I error rate in the second scenario, which is the error rate for the secondary endpoint. It demonstrates that the use of a 1-sided significance level of 0.016 (equivalent to 2-sided level 0.032) for the testing of secondary endpoints at both the interim and final analysis controls the overall type I error rate at the 1-sided level 0.025 regardless of the correlation between the primary and secondary test statistics and the magnitude of treatment effect of the primary endpoint.

**Appendix Figure 2. Type I Error Rate of Secondary Endpoint in a Group Sequential Design with OF Boundaries for Primary Endpoint and 1-sided Significance Level of 0.016 for the Secondary Endpoints with 1 Interim and 1 Final Analysis**

